### 7.2.3.2 Analytical method

Plasma concentrations of dabrafenib and its metabolites hydroxy-dabrafenib (GSK2285403), carboxy-dabrafenib (GSK2298683), and desmethyl-dabrafenib (GSK2167542) and trametinib will be measured using validated liquid chromatography/mass spectrometry/ mass spectrometry (LC/MS/MS) methods. The lower limit of quantification (LLOQ) for dabrafenib, hydroxy-dabrafenib and desmethyl-dabrafenib is 1 ng/mL and 0.25 ng/mL for trametinib for a 50  $\mu$ L aliquot of human plasma. The LLOQ for carboxy-dabrafenib is 5 ng/mL for a 25  $\mu$ L aliquot of human plasma. Concentrations below the LLOQ will be treated as zero.

Meal records must be kept for all patients on PK days as indicated in Table 7-1. The date, start and end time, and percentage consumed for all meals on PK days must be recorded in the CRFs.

[figure not shown]
<sup>b The first Dose Reference ID (DRID no.) is for current dose, while the second DRID no. is for the last dose the patient received prior to the collection of the PK sample.

<sup>c Unscheduled PK samples will be uniquely, sequentially numbered 2001, 2002, etc.

<sup>d Last dose the patient received prior to the collection of the unscheduled PK

e PK samples can be collected anytime between 1-3 hours after the morning dose

f PK samples can be collected anytime between 5-10 hours after the morning dose

### Other assessments

No additional tests will be performed on patients entered into this study.

### 7.2.5 Resource utilization

Not applicable.

# 7.2.6 Patient reported outcomes (LGG cohort only)

Patient reported outcomes (PRO) will be assessed using the PROMIS Parent Proxy Global Health 7+2 for LGG patients. The PRO will measure the patient's overall evaluation of his or her physical, mental, and social health. PRO data will be collected using an electronic tablet device and administered in the patient's local language. Patients should be given the questionnaire to be completed before any clinical assessments are performed. Site personnel must review the questionnaire for completeness, and document patient's refusal to complete all or any part of the questionnaire. Completed questionnaire and any unsolicited comments written by the patient should be reviewed and assessed by the investigator for responses which may indicate potential AEs or SAEs. If AEs or SAEs are confirmed, investigators should not encourage the patient to change responses reported in the completed questionnaire. Investigators must follow reporting instructions outlined in Section 8. Questionnaires are administered according to the Table 7-1 and Table 7-3 until the patient disease progression per RANO criteria.

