|  | Category | Protocol Section | Screening        | (V
± | sse
Vee
2 d | ks | nen
1 to
/isit | 5) | (V | /eeks | s 8 to | ek As
56)
wind |      | ment   | ts  | Every 16
weeks
±7 day visit
window | End of treatment (EoT)
Within 30 days after last dose | Post Treatment Follow up
Every 16 weeks ±14 day visit
window | Ilow up
nths   |
| Week   |          |                  | -28 to -1        | 1       | 2                 | 3  | 4                    | 5  | 8  | 16    | 24     | 32                   | 40   | 48     | 56  | 72,
88-n                                 | End of trea
Within 30 c                               | Post Treatn
Every 16 w
window                                       | Survival follow u |
| Eligibility checklist (within IRT)                   | S        | 7.1.2.1          | Х                |         |                   |    |                      |    |    |       |        |                      |      |        |     |   |  |   |                   |
| IRT Randomization (LGG cohort only)                  | D        | 6.5.2            | X                |         |                   |    |                      |    |    |       |        |                      |      |        |     |   |  |   |                   |
| Patient History                                      |          |                  |                  |         |                   |    |                      |    |    |       |        |                      |      |        |     |   |  |   |                   |
| Demography   | D        | 7.1.2.3          | X                |         |                   |    |                      |    |    |       |        |                      |      |        |     |   |  |   |                   |
| Inclusion/exclusion criteria                         | D        | 5.2, 5.3         | X                |         |                   |    |                      |    |    |       |        |                      |      |        |     |   |  |   |                   |
| Medical History                                      | D        | 7.1.2.3          | X                |         |                   |    |                      |    |    |       |        |                      |      |        |     |   |  |   |                   |

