|                                |          |                  |                  |                 |             |                        |    |       |           |          | ks 31 - 3 |          |          |        |   |  |  |                                      |
|                                |          |                  |                  |                 |             |                        |    |       |           |          | ks 37 - 3 |          |          |        |   |  |  |                                      |
|                                |          |                  |                  |                 |             |                        |    |       |           |          | ks 43 - 4 |          |          |        |   |  |  |                                      |
|                                |          |                  |                  |                 |             |                        |    |       |           |          | ks 49 - 5 |          |          |        |   |  |  |                                      |
|                                |          |                  |                  |                 |             |                        |    |       |           | Weel     | ks 55 - 5 | 7        |          |        |   |  |  |                                      |
| Patient Reported Out           |          |                  | I                |                 | 1           | 1                      | 1  | 1     | 1         |          | T         | T        | 1        | T      | T | T  | Τ  |                                      |
| Parent Proxy Global 7+2 Health | D        | 7.2.6            |                  | X               |             |                        |    | Х     | X         | X        | X         | X        | X        | X      | X | X  | X  |                                      |

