#### 10.5.5 Patient-reported outcomes

Patient reported outcome (PRO) will only be evaluated in the LGG cohort. One PRO questionnaire will be used: the PROMIS Parent Proxy Global Health 7+2. The 7+2 item parent proxy pediatric global health measure include a one global health score plus a single score from pain and a score from fatigue interference item which are scored independently. These two items are administered but do not contribute to the global health score. Rather, they are "signal" items that provide initial score estimates for pain interference and fatigue. Scoring of PRO data and methods for handling of missing items or missing assessments will be according to the scoring manual and user guide for each respective patient questionnaire. No imputation procedures will be applied for missing items or missing assessments. Descriptive statistics will be used to summarize the scored scales of PROMIS Parent Proxy Global Health 7+2 at each scheduled assessment time point for each treatment group. Additionally, change from baseline in the scale at the time of each assessment will be summarized. Subjects with an evaluable baseline score and at least one evaluable post baseline score during the treatment period will be included in the change from baseline analyses. In addition, a repeated measures model for longitudinal data will be used to estimate differences in PROMIS Parent Proxy Global Health 7+2 scores between treatment groups. The number of subjects completing each questionnaire and the number of missing or incomplete assessments will be summarized by treatment group for each scheduled assessment time point. No formal statistical tests will be performed for PRO data and hence no multiplicity adjustment will be applied. The FAS will be used for analyzing PRO data.

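### Section 7.2.6 has patients complete a parent-proxy questionnaire, and its first LGG administration follows open-label randomization, so the change-from-baseline endpoint has no secured respondent and no pre-randomization baseline

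*Protocol*

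**What the plan says.** **Instrument.** Protocol Section 7.2.6 states: "Patient reported outcomes (PRO) will be assessed using the PROMIS Parent Proxy Global Health 7+2 for LGG patients". Section 10.5.5 describes the same instrument as a "7+2 item parent proxy pediatric global health measure".

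**Respondent.** The rest of Section 7.2.6 treats the form as self-report. It says "The PRO will measure the patient's overall evaluation of his or her physical, mental, and social health" and "Patients should be given the questionnaire to be completed before any clinical assessments are performed". Site staff must "document patient's refusal to complete all or any part of the questionnaire", and written comments are also attributed to the patient. No parent or guardian appears outside the instrument's name.

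**Timing.** In Section 7.1, the row "Parent Proxy Global 7+2 Health" of Table 7-3 (chemotherapy arm) is empty at screening and first marked at Week 1. The matching row of Table 7-1 (dabrafenib plus trametinib arm) is the same. The row "IRT Randomization (LGG cohort only") in Table 7-1, and its counterpart in Table 7-3, are marked in the screening column, Day -28 to -1. The text of Section 7.1 equates Week 1 with Day 1, and Section 6.5.3 states that the LGG cohort is open label.

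**Use.** Table 3-1 lists change from baseline in this scale as LGG secondary endpoint 20. Section 10.5.5 summarizes change from baseline by visit, fits a repeated-measures model to estimate arm differences in scores, and rules out formal tests of PRO data.

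**The concern.** Two separate weaknesses bear on the same endpoint.

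The first is who answers. A proxy form records an adult's view of the child. Given to a teenager, it records something else. If one site follows the text and another follows the instrument's title, the scores are not one measure. If the respondent changes between visits, part of a within-child change is a change of rater.

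The second is when the first score is taken. By Day 1 the family can know whether the child will receive oral drugs or intravenous chemotherapy lasting about 60 weeks (12 weeks of induction including rest, plus 8 cycles of 6 weeks: 12 + 48 = 60; Section 6.1.2). Relief or disappointment at the assignment can colour the rating that later serves as baseline.

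Neither can be repaired at analysis. A statistical analysis plan can define baseline, but it cannot supply a pre-randomization score that was never collected, nor recover who filled in a form if that was not recorded.

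**Working it through.** The protocol gives no standard deviation, expected change or sizing for this endpoint, so there is no figure to reproduce. The check sets the sections side by side and then follows a baseline shift through the planned analyses.

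**1. Can the respondent instruction be followed?** Section 5.2 admits patients from 12 months to under 18 years. The youngest cannot complete a questionnaire, so an adult must, contrary to the wording of 7.2.6. The oldest can comply, but would then be answering a form written for a parent. The section sets no age rule, no same-respondent rule and no field for the respondent's identity. Elsewhere the protocol names the adult when it means the adult: Sections 4.1 and 4.1.2.1 write patient/legal guardian, and Section 6.6 adds caregivers.

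**2. Does any scheduled score precede randomization?**
- Randomization, Tables 7-1 and 7-3: screening column, Day -28 to -1.
- First questionnaire, Tables 7-1 and 7-3: Week 1, that is Day 1.
- Questionnaire at screening: none, in either arm.

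So no pre-randomization score is scheduled for any LGG patient. Section 7.2.6 puts the form before clinical assessments, so the Day 1 score is probably also pre-dose. The issue is knowledge of the arm, not a drug effect.

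**3. Where would an arm-related shift go?** Let d be the difference between arms in the mean Day 1 score that is caused only by knowing the assignment. Let D be the difference between arms in mean score at a later visit. Randomization makes the arms equal in expectation before assignment.
- Raw change from baseline: difference between arms = D - d. The shift enters in full.
- Model of scores with baseline as a covariate, coefficient b: difference = D - b × d. The shift enters in part when b lies between 0 and 1.
- Model of scores without baseline: difference = D. The shift does not enter through the baseline.

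Section 10.5.5 models scores and summarizes change, and does not say how baseline enters the model.

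**4. Can the direction be given?** Suppose a fraction r of the shift persists at the later visit. Its net contribution to the raw change difference is then (r - 1) × d with a Day 1 baseline and r × d with a pre-randomization baseline. With r = 1 the Day 1 baseline cancels it; with r = 0 the pre-randomization baseline is clean and the Day 1 baseline carries -d. The documents give neither d nor r, so neither size nor direction can be computed.

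**5. How many patients could still benefit?** At Amendment 5, 44 of about 102 LGG patients had been randomized: 44/102 = 43%. That leaves 102 - 44 = 58.

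**The case against.** The strongest reply on the respondent is that the word patient is used loosely. Section 7.2.7 likewise has all patients on the liquid formulations complete a palatability questionnaire, in a trial that enrols from 12 months. The instrument is called Parent Proxy throughout, and Section 10.5.5 defers scoring and missing-data handling to the questionnaire's manual and user guide. This stands in part. A reader might infer that the protocol instructs adolescents to answer for themselves and parents to answer for toddlers, or that raters will change between visits. It does neither. Mixing is a foreseeable result of an unworkable instruction, and it affects only children for whom the wrong or a different person answers.

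On the baseline, a reader might infer that the shift carries one-for-one into the estimated treatment difference for all 102 patients. The documents do not support that. Full carry-over holds for raw change only; the repeated-measures model is of scores, with baseline handling unstated. Families also know the arm at every later visit, so a persistent shift could cancel under a Day 1 baseline and remain under an earlier one.

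Day 1 also has a real advantage: it is the score closest to the start of treatment, whereas a screening score can be up to 28 days old. Finally, PRO data carry no formal test and lie outside the ORR, PFS, OS hierarchy in Section 10.5. These limits stand and bound the importance of the point. They do not remove the contradiction in 7.2.6 or the absence of a pre-randomization score.

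**Conclusion.** The point holds in this limited form. Section 7.2.6 contradicts its own instrument and cannot be carried out for the youngest patients, and it neither names nor records the respondent. The schedules provide no score before open-label randomization, so the baseline of LGG secondary endpoint 20 can be influenced by knowledge of the arm. The absence of a pre-randomization score applies to the whole LGG cohort as scheduled; the bias that results has no computable size or direction. This rests on the table marks as printed, on families knowing the arm by Day 1, and on the Day 1 score serving as baseline because no earlier one exists.

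It would be wrong to conclude that the trial's main result is at risk. The endpoint is secondary and used for description and estimation only, and the primary ORR comparison does not depend on it. The change is worth making because both defects arise at data collection and cannot be mended afterwards.

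**What to change.** **Section 7.2.6.** Replace the patient with the parent or legal guardian as respondent throughout, including the sentences on refusal and comments. Ask for the same person at each visit where possible, and record who answered each time.

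**Tables 7-1 and 7-3.** Add a questionnaire at screening, completed before IRT randomization, and keep the Day 1 questionnaire. Patients with both scores then allow a direct comparison between arms of the change from screening to Day 1, which shows whether knowledge of the arm moved the rating.

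**Patients already randomized (44 at Amendment 5).** Keep Day 1 as baseline, flag it as post-randomization, and report a sensitivity analysis by baseline type. Simply excluding them would discard at least 43% of a cohort whose control arm is planned at about 34 (102/3).

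**Cost.** The change needs revised wording in one section and one added mark in each of two tables, using the existing tablet at an existing visit. The downsides are some questionnaires from families who then fail screening, a screening score that may precede first dose by up to 28 days, and two baseline types within one cohort. The number who can still give a pre-randomization score is at most about 58 and falls with every patient randomized before the change takes effect.

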# 7.2.7 Acceptability and Palatability Questionnaires

All patients who receive the dabrafenib oral suspension and/or trametinib oral solution will complete the respective questionnaire to evaluate the palatability and acceptability/tolerability of the pediatric formulations. The dabrafenib oral suspension and trametinib oral solution questionnaires must be completed after the dosing of dabrafenib with trametinib according to Table 7-1.

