# 6.1.1 Dabrafenib and Trametinib Dosing regimen

Dabrafenib (DRB436) will be administered orally, twice daily based on weight, age and the appropriate dose level. Trametinib (TMT212) will be administered orally, once daily in combination with the first daily dose of dabrafenib based on weight. A dosing nomogram based on weight and/or age will be used to prescribe dabrafenib (DRB436) and trametinib (TMT212) to minimize inter-patient dosing variability. Dabrafenib is available as capsules and as dispersible tablets for oral suspension (Table 6-1, Table 6-2, Table 6-3 and Table 6-4) and trametinib is available as tablets and as a powder in bottle for oral solution (Table 6-5, Table 6-6, Table 6-7 and Table 6-8).

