#### 6.1.1.1 Dabrafenib (DRB436) and trametinib (TMT212) dosing

Study medications should be taken as follows:

- Dabrafenib will be administered twice daily per the dosing regimen shown in Table 6-1, Table 6-2, Table 6-3 and Table 6-4.
- Trametinib will be administered once daily per the dosing regimen shown in Table 6-5, Table 6-6, Table 6-7 and Table 6-8.
- Trametinib should be taken in combination with dabrafenib once daily, preferably in the morning.
- Dabrafenib capsules and trametinib tablets should be taken with approximately 120-240 mL of water.
- Trametinib pediatric oral solution formulation will be administered with a graduated syringe. Please refer to the trametinib oral solution Instructions for Use.
- Dabrafenib pediatric oral suspension formulation administration will be administered using dosing cup and/or graduated syringe. Please refer to dabrafenib oral suspension Instructions for Use.
- Refer to the dabrafenib and trametinib Instructions for Use documents if enteral feeding tubes are required for administering pediatric oral solutions.
- Patients less than 12 years of age who weigh less than 16 kg must be administered the dabrafenib dispersible tablets for oral suspension.
- Patients equal to or greater than 12 years of age who weigh less than 19 kg must be administered the dabrafenib dispersible tablets for oral suspension.
- Patients less than 6 years old who weigh less than 26 kg must be administered the trametinib oral solution.
- Patients older than 6 years old must weigh at least 33 kg to be administered the trametinib tablets.
- Patients should be encouraged to take dabrafenib at approximately 12 hour intervals and at similar times each day.
- Study treatment should be administered under fasting conditions, at least 1 hour before or 2 hours after a meal.
- If it is not possible for a patient to tolerate the fasting conditions noted above, study treatment may be administered with a small non-fat meal (e.g. small amount of apple juice/sauce, a piece of dry toast). Patients and their guardians should be advised to avoid administering study drug with milk or high-fat, high-calorie foods.
- Patients who are being breastfed may continue to be breastfed on demand. If the patient is breastfed during collection of PK samples the time of breastfeeding should be recorded as a meal.

- If a patient vomits after taking study drug, the patient should be instructed not to retake the dose and wait for the next scheduled dose.

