#### 10.5.1.7 Palatability

Data on palatability assessments (bitterness, sweetness, texture and overall taste) will be summarized and listed.

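### Patients who take both liquid formulations rate each one only after swallowing both, so taste carry-over between the two palatability ratings is uncontrolled

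*Protocol*

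**What the plan says.** The secondary objectives in Section 3 (Table 3-1) include palatability in both cohorts, with questionnaire data as the endpoint. The protocol summary names the dabrafenib oral suspension and the trametinib oral solution.

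Section 7.2.7 says who fills in what: "All patients who receive the dabrafenib oral suspension and/or trametinib oral solution will complete the respective questionnaire". It then sets the timing of both forms in one sentence: "The dabrafenib oral suspension and trametinib oral solution questionnaires must be completed after the dosing of dabrafenib with trametinib according to Table 7-1". Table 7-1 gives each form its own row and schedules both at Weeks 1 and 5 only.

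On dosing, Section 6.1.1 states: "Trametinib (TMT212) will be administered orally, once daily in combination with the first daily dose of dabrafenib based on weight". Section 6.1.1.1 repeats the point: "Trametinib should be taken in combination with dabrafenib once daily, preferably in the morning". On the analysis, Section 10.5.1.7 says: "Data on palatability assessments (bitterness, sweetness, texture and overall taste) will be summarized and listed".

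**The concern.** Two product-specific questionnaires exist so that a score can be credited to one product. Bitterness, sweetness, texture and overall taste are sensory ratings, and an aftertaste from one liquid can colour the rating of another swallowed shortly before or after it. If both forms follow the joint dose, and no order, interval or rinse is stated, a low score for one formulation may partly reflect the other.

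This is a matter of data collection and not something left to the statistical analysis plan. The protocol itself fixes when the forms are completed. Once both ratings are taken after both tastes, no later analysis can separate them. The children most exposed are the lightest ones, who have no capsule or tablet alternative.

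**Working it through.** The plan gives no figure to reproduce, so the check sets the passages side by side.

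**1. When is each rating taken?** Section 7.2.7 places both forms after dabrafenib has been dosed with trametinib. Sections 6.1.1 and 6.1.1.1 put the two drugs at the same dosing occasion. For a child on both liquids this gives 2 forms × 2 visits = 4 scheduled ratings. Read as written, none of the 4 precedes the tasting of the other product. The second daily dabrafenib dose is taken without trametinib, but neither form is tied to it.

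**2. Who is affected?** The formulation rules are in Sections 6.1.1 and 6.1.1.1.

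| Group | Dabrafenib | Trametinib |
|---|---|---|
| Under 6 years, below 16 kg | suspension mandatory | solution mandatory (limit 26 kg) |
| 6 to under 12 years, below 16 kg | suspension mandatory | solution mandatory (limit 33 kg) |
| 12 years or older, below 19 kg | suspension mandatory | solution mandatory (limit 33 kg) |
| At or above the dabrafenib limit, below the trametinib limit | capsule or suspension | solution mandatory |
| At or above both limits | capsule or suspension | tablet or solution |

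The first three rows always take both liquids. The last two rows take both only by choice. A child on one liquid plus a capsule or tablet tastes one liquid, so the problem does not arise. Patients who cross over from chemotherapy complete no taste questionnaires (Section 4.1.2.2). The protocol does not give the number taking both liquids. It could be few or most.

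**3. Is the order known?** Section 7.2.3 requires exact dosing times on the eCRF, and Table 7-6 gives the two drugs separate dose references on Week 1 Day 1. For patients with full sampling who have Day 1 samples, the order might be recovered if the two times differ. Patients under 10 kg have no Day 1 sample in Table 7-6. The sparse schedule (Table 7-7) starts at Week 3. No pharmacokinetic sample is scheduled at Week 5 for anyone.

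**4. Would separating the ratings disturb the pharmacokinetic windows?** On Day 1 one blood draw serves both drugs, with windows of ±5 minutes at 0.5 and 2 hours and ±20 minutes at 4 hours. Assume the window applies to each drug's own dose. With a gap of g minutes between the drugs, the 0.5-hour draw at time t after the first must satisfy 25 ≤ t ≤ 35 and 25 ≤ t − g ≤ 35, so 25 + g ≤ t ≤ 35. This is possible only if g ≤ 10. If the draw is timed at exactly 30 minutes after the first drug, then 30 − g ≥ 25, so g ≤ 5. A short pause can fit, but it has to be planned. At Week 5 there is no such constraint.

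**The case against.** The strongest reply is that the two products are handled separately. The trametinib liquid has a graduated syringe ("Trametinib pediatric oral solution formulation will be administered with a graduated syringe") and the dabrafenib liquid its own device ("Dabrafenib pediatric oral suspension formulation administration will be administered using dosing cup and/or graduated syringe"). Each has its own form. Nothing says that the liquids are mixed. A reader might infer that the endpoint measures a blend of two tastes, or that no rating can be credited to either product. The documents do not support that. A child or parent can still distinguish two liquids swallowed one after the other. What stands is possible carry-over and misattribution, not a measured mixture.

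A reader might also infer that every palatability rating is affected, or that the order of the drugs is never recorded. Neither holds. Patients on one liquid are unaffected, and Day 1 dosing times exist for part of the cohort.

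The Instructions for Use, the questionnaires and the eCRF are not shown, and they may set an order or a rinse. That leaves room for doubt, but Section 7.2.7 still places both forms after both drugs.

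It can further be said that the forms also cover acceptability, which is reasonably judged under the conditions of use. That is fair for acceptability and less so for bitterness, sweetness and texture of a named product. Finally, a pause on Day 1 could push a blood sample out of its window. That objection is sound and limits the fix.

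**Conclusion.** The point holds in a limited form. For patients who take both the suspension and the solution, the protocol times both taste questionnaires after the joint dose, so each rating is open to uncontrolled carry-over from the other product. It covers both scheduled visits for these patients and includes every child for whom both liquids are mandatory. Patients on one liquid are not affected.

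The consequence is minor. Palatability is summarised and listed without a test or threshold, and nothing in the response-rate analyses depends on it. The size of the distortion cannot be calculated from the protocol, because neither the share on both liquids nor any taste data are given.

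The conclusion assumes that Section 7.2.7 is applied as written and that the documents not shown do not override it.

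**What to change.** In Section 7.2.7, state that each questionnaire is completed directly after its own product is swallowed. Where both are liquid, the first form is completed before the second product is tasted, and the second form directly after the second product. Apply this at Week 5, and on Day 1 only where the sampling windows of Table 7-6 are kept. Record on the eCRF which product was taken first. In Section 10.5.1.7, summarise palatability by one versus both products taken as liquid and, among the latter, by order. No dose, frequency or co-administration rule changes.

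The product taken first is then rated without the other's taste from that dosing occasion. The second may still carry some aftertaste, but its position is known. Order is not randomised, so the comparison by order stays descriptive.

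The cost is a short amendment to two sections, one eCRF field and a pause of a few minutes at the questionnaire visits. The form must also be at hand when the Week 5 dose is taken. Section 7.2.2.3 already puts vital signs before study medication on each assessment day, so this should fit within the visit.
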